### Tertiary/Exploratory Objectives

- *To compare additional PK parameters of PF-06651600 following administration of multiple oral doses in participants with renal impairment and in healthy participants without renal impairment.*
- *To enable exploratory research through collection of banked biospecimens, unless prohibited by local regulations or ethics committee decision.*

## 3. INTERIM ANALYSES, FINAL ANALYSES AND UNBLINDING

*No formal interim analysis will be conducted for this study. As this is an open-label study, the sponsor may conduct unblinded reviews of the data during the course of the study for the purpose of safety assessment.*

*Additionally, PK data will be analyzed in Part 1 and based on the results decision will be made whether to progress to Part 2.*

Final analysis will follow the official database release. As this will be an open-label study, there is no formal unblinding of the randomization code.

## 4. HYPOTHESES AND DECISION RULES

### 4.1. Statistical Hypotheses

No hypotheses are required.

### 4.2. Statistical Decision Rules

After statistical evaluation of results from Part 1 (see Section 9.4 in the protocol), Part 2 will be conducted if the point estimate of PF-06651600 area under the concentration-time curve from time 0 to 24 hours ( $AUC_{0-24}$ ) geometric mean ratio (GMR) for the severe renal impairment group (compared to the normal group as control) is  $\geq 2.0$ . If this criterion is not met, the study will stop after Part 1.

## **5. ANALYSIS SETS**

### **5.1. Pharmacokinetic (PK) Analysis Set**

#### **5.1.1. Concentration Analysis Set**

*The PK concentration population is defined as all participants assigned to investigational product and treated who have at least 1 concentration measured.*

#### **5.1.2. Parameter Analysis Set**

*The PK parameter analysis population is defined as all participants assigned to investigational product and treated who have at least 1 of the PK parameters of primary interest measured.*

### **5.2. Pharmacodynamic Analysis Set**

None.

### **5.3. Safety Analysis Set**

*All assigned to investigational product and who take at least 1 dose of investigational product. Participants will be analyzed according to the product they actually received.*

### **5.4. Other Analysis Sets**

None.

### **5.5. Treatment/Group Misallocations**

All analyses will be performed on an “as-treated” basis and will not include data from subjects who are randomized but not treated.

If based on eGFR value(s) a subject is assigned to the wrong renal impairment group, this subject will be reassigned to the correct group and analyzed for safety and PK analysis according to his reassigned group.

### **5.6. Protocol Deviations**

Subjects who experience events that may affect their PK profile (eg, lack of compliance with dosing) may be excluded from the PK analysis. At the discretion of the pharmacokineticist a concentration value may also be excluded if the deviation in sampling time is of sufficient concern or if the concentration is anomalous for any other reason.

A full list of protocol deviations will be compiled and reviewed to identify major and minor deviations prior to database closure.

#### **5.6.1. Deviations Assessed Prior to Randomization**

At Screening, the investigator will assess subjects against the inclusion and exclusion criteria as set out in Sections 4.1 and 4.2 of the protocol.

### **5.6.2. Deviations Assessed Post-Randomization**

A full list of protocol deviations for the study report will be compiled prior to database closure. Any significant deviation from the protocol will be reviewed prior to database closure and a decision taken regarding evaluation for each analysis population.

## **6. ENDPOINTS AND COVARIATES**

### **6.1. Efficacy Endpoint(s)**

None.

### **6.2. Safety Endpoints**

An adverse event is considered a Treatment-Emergent Adverse Event (TEAE) if the event started during the effective duration of treatment.

All events that start on or after the first dosing day and time/start time, if collected, but before the last dose plus the lag time will be flagged as TEAEs.

The following data are considered in standard safety summaries (see protocol for collection days and list of parameters):

- *adverse events,*
- *laboratory data,*
- *vital signs data,*
- *ECG results.*

### **6.3. Other Endpoints**

#### **6.3.1. PK Endpoints**

Blood and urine samples for PK analysis of PF-06651600 will be taken according to the Schedule of Activities given in the protocol.

The following PK parameters will be calculated for PF-06651600 (if possible) from the concentration-time data using standard noncompartmental methods:

**Table 3. Noncompartmental PK Parameters**

| Matrix | PK Parameter                 | Analysis Scale | PF-06651600 |
|--------|------------------------------|----------------|-------------|
| Plasma | AUC 0-24          | ln             | A, D        |
|        | AUC last          | ln             | D           |
|        | C max             | ln             | A, D        |
|        | T max             | R              | D           |
|        | CL/F                         | ln             | D           |
|        | C trough          | ln             | D           |
| Urine* | CL r † | ln             | D           |
|        | Ae 24             | R              | D           |
|        | Ae 24 (%)         | R              | D           |

Key: A=analyzed using statistical model, D=displayed with descriptive statistics, ln=natural-log transformed, R=raw (untransformed), \* =will be analyzed depending on Plasma PK results.

### 6.3.2. PD Endpoints

None.

### 6.4. Covariates

None.

## 7. HANDLING OF MISSING VALUES

For the analysis of safety endpoints, the sponsor data standard rules for imputation will be applied.

### 7.1. Concentrations Below the Limit of Quantification

In all data presentations (except listings), concentrations below the limit of quantification (BLQ) will be set to zero. (In listings BLQ values will be reported as “<LLQ”, where LLQ will be replaced with the value for the lower limit of quantification).

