4.3. Justification for Dose

The study will use the PF-06651600 dose of 50 mg QD, given orally for up to 10 days. The choice of this dose is based on the highest maintenance dose of PF-06651600 currently being evaluated in Phase 3 AA and vitiligo programs. Based on the short half-life (arithmetic mean of 1.13 hours for 50 mg dose in B7981001 study), steady state is expected to be achieved within a day. However, a dosing period of 10 days was used to ensure that if there is a potential for time-dependent CYP3A4 enzyme inhibition due to PF-06651600, it can be fully observed.

Doses of PF-06651600 higher than 50 mg QD have demonstrated their safety and tolerability for up to 14 days (dose of 400 mg QD) in healthy participants (B7981001), and up to 24 weeks (dose of 50 mg QD) in participants with AA (B7931005). The dose of 200 mg QD has demonstrated safety and tolerability for up to 8 weeks in RA participants (B7981006) (Section 2.2.4.2.2). CCI

[REDACTED]

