**Table 1. Renal Function Categories by eGFR Ranges**

| Cohort | Renal Impairment a | Estimated eGFR b (mL/min) | Number of Participants |
|--------|-------------------------------|--------------------------------------|------------------------|
| 1      | Severe Renal Impairment       | <30 and not requiring dialysis       | 8                      |
| 2      | None (Normal)                 | ≥90                                  | 8                      |
| 3      | Moderate renal impairment     | ≥30 to <60                           | 8                      |
| 4      | Mild Renal Impairment         | 60 - 89                              | 8                      |

- a. Stages of renal impairment are based on Kidney Disease Outcomes Quality Initiative (KDOQI) Clinical Practice Guidelines for Chronic Kidney Disease (CKD).
- b. Estimate of eGFR based on Modification of Diet in Renal Disease (MDRD) formula. The average of the 2 screening eGFR value will be used for group assignment.
- Step 1:  $eGFR (mL/min/1.73m^2) = 175 \times (S_{cr, std})^{-1.154} \times (Age)^{-0.203} \times (0.742 \text{ if female}) \times (1.212 \text{ if African American})$  where  $S_{cr, std}$  denotes serum creatinine measured with a standardized assay.
  - Step 2: Convert the MDRD-derived, body surface area (BSA)-adjusted eGFR obtained above to absolute eGFR (mL/min) for eligibility assessment using the following equation:  
 $eGFR (mL/min) = eGFR (mL/min/1.73m^2) \times \text{participant's BSA}$  where BSA is calculated as  $BSA = (Weight^{0.425} \times Height^{0.725}) \times 0.007184$ .

**Part 1:** A total of approximately 16 participants will be enrolled in Part 1; approximately 8 participants with severe renal impairment and approximately 8 with normal renal function to ensure at least 6 evaluable participants in each group. Participants from the severe renal impairment group will be recruited first. The demographics will be pooled across study sites to determine an average value for age and weight in the severe impairment group. Subsequently, the healthy participants will be recruited later such that each participant's age is within ±10 years and weight is within ±15 kg of the mean of severe renal impairment

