### 7.2. Deviations, Missing Concentrations and Anomalous Values

In summary tables and plots of median profiles, statistics will be calculated having set concentrations to missing if 1 of the following cases is true:

1. A concentration has been collected as ND (ie, not done) or NS (ie, no sample).
2. A deviation in sampling time is of sufficient concern or a concentration has been flagged anomalous by the pharmacokineticist.

Note that summary statistics will not be presented at a particular time point if more than 50% of the data are missing.

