### 7.3. Pharmacokinetic Parameters

Actual PK sampling times will be used in the derivation of PK parameters.

If a PK parameter cannot be derived from a subject's concentration data, the parameter will be coded as NC (ie, not calculated). (Note that NC values will not be generated beyond the day that a subject discontinues).

In summary tables, statistics will be calculated by setting NC values to missing; and statistics will be presented for a particular renal function group with  $\geq 3$  evaluable measurements. For statistical analyses (ie, analysis of variance), PK parameters coded as NC will also be set to missing; and analyses will not be performed for a particular parameter if more than 50% of the data are NC.

If an individual subject has a known biased estimate of a PK parameter (due for example to an unexpected event such as vomiting before all the compound is adequately absorbed in the body), this will be footnoted in summary tables and will not be included in the calculation of summary statistics or statistical analyses.

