**Table 4. PK Parameters to be Summarized Descriptively by Group**

| Parameter                                                                      | Summary Statistics                                                                                       |
|--------------------------------------------------------------------------------|----------------------------------------------------------------------------------------------------------|
| $AUC_{last}$ , $AUC_{0-24}$ ,
$C_{max}$ , $C_{trough}$ , $CL_r$ ,
$CL/F$ | N, arithmetic mean, median, cv%, standard deviation, minimum, maximum, geometric mean and geometric cv%. |
| $T_{max}$                                                                      | N, median, minimum, maximum.                                                                             |
| $Ae_{24}$ , $Ae_{24}(\%)$                                                      | N, arithmetic mean, median, cv%, standard deviation, minimum, maximum.                                   |

Presentations for PF-06651600 concentrations will include:

- a listing of all concentrations sorted by renal function group (present in heading), subject id and nominal time postdose. The concentration listing will also include the actual times. Deviations from the nominal time will be given in a separate listing.
- a summary of concentrations by renal function group and nominal time postdose, where the set of statistics will include n, mean, median, standard deviation, coefficient of variation (cv), minimum, maximum and the number of concentrations above the lower limit of quantification.
- median concentrations time plots (on both linear and semi-log scales) against nominal time postdose by renal function group (all renal function groups on the same plot per scale, based on the summary of concentrations by renal function group and time postdose).
- mean concentrations time plots (on both linear and semi-log scales) against nominal time postdose by renal function group (all renal function groups on the same plot per scale, based on the summary of concentrations by renal function group and time postdose).
- individual concentration time plots by renal function group (on both linear and semi-log scales) against actual time postdose (there will be separate spaghetti plots for each renal function group per scale).

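### Does setting BLQ concentrations to zero make the C_trough geometric mean and geometric CV% in SAP Table 4 unworkable?

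*SAP*

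**What the plan says.** SAP Section 7.1 gives the rule for concentrations below the limit of quantification (BLQ): "In all data presentations (except listings), concentrations below the limit of quantification (BLQ) will be set to zero". Listings show them as below the lower limit of quantification (LLQ) instead.

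Protocol Table 3 takes C_trough straight from the pre-dose samples, with no derivation. SAP Table 3 places it on the ln scale and marks it D, for descriptive display only. SAP Table 4 puts it in the same row as AUC0-24, AUC_last, Cmax, CL/F and CL_r, with these statistics: "N, arithmetic mean, median, cv%, standard deviation, minimum, maximum, geometric mean and geometric cv" (the last being geometric CV%).

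Two other SAP sections deal with values that drop out. Section 7.2 sets to missing samples that were not done or not available, and values with a worrying sampling time or an anomaly flag. Section 7.3 codes a parameter that cannot be derived as not calculated (NC) and adds: "In summary tables, statistics will be calculated by setting NC values to missing". Neither mentions a BLQ trough. The reference to sponsor standard imputation rules at the head of Section 7 is limited to safety endpoints.

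The separate summary of concentrations in SAP 8.2 asks for no geometric statistics. Its list ends with "minimum, maximum and the number of concentrations above the lower limit of quantification".

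**The concern.** Read together, these sections seem to ask for something that cannot be computed. A BLQ trough becomes 0 under Section 7.1, and Table 4 then wants statistics that need its logarithm. A programmer would have to choose between leaving the geometric statistics blank, computing them on the quantifiable values only (with a smaller N), or substituting a positive value. The SAP does not choose, and the printed figures would depend on the choice.

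BLQ troughs are also plausible here. Protocol 4.3 argues: "Based on the short half-life (arithmetic mean of 1.13 hours for 50 mg dose in B7981001 study"), and dosing is once daily. If the row fed a comparison or a decision, an unstated convention chosen after seeing the data would be a proper objection.

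**Working it through.** The documents give no figure of their own on this point, so there is none to reproduce. The check has four steps.

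**1. What one zero does.** Geometric mean = exp(mean of ln x). Geometric CV% = 100 × sqrt(exp(variance of ln x) − 1). With one x = 0, ln x is minus infinity. The variance, and so the geometric CV%, has no value. The geometric mean is undefined through logs and equals 0 as the n-th root of the product. The arithmetic statistics, median, minimum and maximum can still be computed.

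**2. How likely a BLQ trough is.** Inputs: half-life 1.13 h (protocol 4.3) and a 24 h dosing interval.
- 24 / 1.13 = 21.2 half-lives; fraction remaining 2^(−21.2) = 4.0 × 10⁻⁷.
- The LLQ is not given. Assuming a Cmax/LLQ ratio of 100, 1,000 or 10,000, the concentration reaches the LLQ after 1.13 × log2(ratio) = 7.5, 11.3 or 15.0 h. A quantifiable 24 h trough would then need a half-life of 24 / log2(ratio) = 3.6, 2.4 or 1.8 h.
- This assumes simple exponential decline at the cited half-life. Protocol 4.2 warns that single-dose behaviour does not predict multiple-dose PK here, so the BLQ rate cannot be fixed from the documents.

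For group size, SAP 2.1 plans "approximately 8 with normal renal function to ensure at least 6 evaluable participants in each group". With an assumed, independent BLQ probability p per trough, P(at least one BLQ in the group) = 1 − (1 − p)^n:

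| p | n = 6 | n = 8 |
|---|---|---|
| 0.05 | 0.26 | 0.34 |
| 0.10 | 0.47 | 0.57 |
| 0.25 | 0.82 | 0.90 |
| 0.50 | 0.98 | 0.996 |

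**3. How much the convention changes the printed row.** Assumed data: 0.8, 1.0, 1.3, 1.6, 2.0, 2.5, 3.0 and one BLQ, with LLQ 0.5.

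| BLQ value | Geometric mean | Geometric CV |
|---|---|---|
| Kept as 0 | undefined (0 by product) | undefined |
| Dropped (N = 7) | 1.58 | 51% |
| Set to LLQ | 1.37 | 66% |
| Set to LLQ/2 | 1.26 | 93% |

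With the zero kept, the arithmetic mean is 12.2 / 8 = 1.525, the arithmetic CV 63% and the median (1.3 + 1.6) / 2 = 1.45.

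**4. Where the row leads.** Protocol Section 3 lists C_trough under the tertiary/exploratory endpoints. SAP Table 3 marks only AUC0-24 and Cmax for the statistical model. The Part 2 rule in SAP 4.2 uses the AUC0-24 geometric mean ratio against 2.0. The Part 2 regressions in SAP 8.2 use CL/F or CL_r and V_z/F. No planned model, ratio or decision takes C_trough as input.

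**The case for a change.** The best case for a change is this. The conflict is in the text and can be met with a sentence. It is likely to occur. The convention visibly alters the numbers, as step 3 shows. It can even decide whether the row appears: SAP 7.3 presents statistics only for groups with at least 3 evaluable measurements, so a group of 8 with 6 BLQ troughs has a full row if zeros are kept and none if they are treated as NC. The count of quantifiable values sits in the concentration summary and not in the C_trough row.

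Most of that is correct as description. Three qualifications reduce its force. First, the SAP is not wholly silent: C_trough is listed as a PK parameter, and Section 7.3 lets a parameter be coded NC and set to missing. That is the weaker reading, since the trough is observed and Section 7.1 gives it a value, but an analyst could defend it. Second, if zeros are kept, the row's own minimum of 0 reveals a BLQ value; if they are dropped, the lower N is a signal. Third, choosing a convention late matters when it can favour a result, and here no test, ratio or threshold on C_trough exists to be favoured.

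A related wording slip adds no weight. Protocol Section 3 lists C_trough on Days 8 to 11, while protocol 4.1 and Table 3 give Days 8 to 10. The PK sampling schema includes a Day 11 sample, at the end of the 24 h sampling after the Day 10 dose, so no data are at risk. It is clerical and has nothing to do with BLQ handling.

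**Conclusion.** No change to the plan follows. This is missing detail that analysts will fill sensibly. Anyone programming the table meets the zero as soon as a log is taken, and either reports the geometric statistics as not calculated or states the basis in a footnote. The reader can verify either from the listings and the count of quantifiable concentrations.

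The size is at most two descriptive statistics for one tertiary parameter, in whichever groups and days have a BLQ trough. At the extremes the convention hardly matters. If the 1.13 h half-life held at steady state, nearly all troughs would be BLQ and no convention would give an informative geometric mean. If troughs lie well above the LLQ, the question never arises. Only the range between leaves a choice, and its likelihood depends on the LLQ and the steady-state concentrations, which the documents do not give. Anywhere in that range, the AUC0-24 and Cmax comparisons and the decision on Part 2 come out the same.

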### 7.2. Deviations, Missing Concentrations and Anomalous Values

In summary tables and plots of median profiles, statistics will be calculated having set concentrations to missing if 1 of the following cases is true:

1. A concentration has been collected as ND (ie, not done) or NS (ie, no sample).
2. A deviation in sampling time is of sufficient concern or a concentration has been flagged anomalous by the pharmacokineticist.

Note that summary statistics will not be presented at a particular time point if more than 50% of the data are missing.

### 7.3. Pharmacokinetic Parameters

Actual PK sampling times will be used in the derivation of PK parameters.

If a PK parameter cannot be derived from a subject's concentration data, the parameter will be coded as NC (ie, not calculated). (Note that NC values will not be generated beyond the day that a subject discontinues).

In summary tables, statistics will be calculated by setting NC values to missing; and statistics will be presented for a particular renal function group with  $\geq 3$  evaluable measurements. For statistical analyses (ie, analysis of variance), PK parameters coded as NC will also be set to missing; and analyses will not be performed for a particular parameter if more than 50% of the data are NC.

If an individual subject has a known biased estimate of a PK parameter (due for example to an unexpected event such as vomiting before all the compound is adequately absorbed in the body), this will be footnoted in summary tables and will not be included in the calculation of summary statistics or statistical analyses.

## **8. STATISTICAL METHODOLOGY AND STATISTICAL ANALYSES**

### **8.1. Statistical Methods**

The effect of the renal impairment on PK parameters will be assessed by constructing 90% confidence intervals around the estimated difference between each of the Test (renal impaired groups) and the Reference (normal renal function group) using a one-way ANOVA model based on natural log transformed data.

The relationship between PK parameters and renal function will be assessed using linear regression model.

### **8.2. Statistical Analyses**

#### **Part 1**

*Analysis of variance (ANOVA) will be used to compare the natural log transformed PF-06651600  $AUC_{0-24}$  and  $C_{max}$  between normal renal function group (Reference) and the severe impaired renal function group (Test). Estimates of the adjusted mean differences (Test-Reference) and corresponding 90% confidence intervals (CIs) will be obtained from the model. The mean differences and 90% CIs for the differences will be exponentiated to provide estimates of the ratio of the geometric means (Test/Reference) and 90% CIs for the ratios.*

*Part 2 may be conducted if PF-06651600  $AUC_{0-24}$  GMR for severe renal impairment group compared to normal group is  $\geq 2$ .*

#### **Part 2**

*ANOVA will be used to compare the natural log transformed PF-06651600  $AUC_{0-24}$  and  $C_{max}$  between normal renal function group (Reference) and the moderate and mild impaired renal function groups (Test). Estimates of the adjusted mean differences (Test-Reference) and corresponding 90% CIs will be obtained from the model. The mean differences and 90% CIs for the differences will be exponentiated to provide estimates of the ratio of the geometric*

means (Test/Reference) and 90% CIs for the ratios. If substantial differences in demographic characteristics between healthy and impaired participants are observed, weight and age will be explored as covariates.

Box and whisker plots for individual participant parameters ( $AUC_{0-24}$  and  $C_{max}$ ) will be constructed by renal function group and overlaid with geometric means.

For summary statistics and median/mean plots by sampling time, the nominal PK sampling time will be used. For individual participant plots by time, the actual PK sampling time will be used.

If Part 2 is executed and data for normal, mild, moderate and severe impairment groups are available, additional analysis will be performed to assess relationship between appropriate PK parameters and renal function.

Linear regression will be used to analyze the potential relationship between appropriate PK parameters ( $CL/F$  or  $CL_r$ , and  $V_z/F$ ) and renal function (eGFR). Estimates of the slope and intercept, together with their precision (90% CI), and the coefficient of determination will be obtained from the model.

Plots of PK parameters ( $CL/F$  or  $CL_r$ , and  $V_z/F$ ) versus renal function (eGFR) will be constructed. A regression line and 90% confidence region for the PK parameters and eGFR will be included if appropriate. Vertical lines for the renal function group cut-off values will also be presented on the plots. Different symbols will be used to identify participants from different renal function groups.

Residuals from the models will be examined for normality and the presence of outliers via visual inspection of plots of residuals vs predicted values and normal probability plots of residuals but these will not be included in the clinical study report. If there are major deviations from normality or outliers then the effect of these on the conclusions will be investigated through alternative transformations and/or analyses excluding outliers. Justification for any alternative to the planned analysis will be given in the report of the study.

The following PK parameters will be summarized by renal function group:

